3.2. Inclusion Criteria

Potential subjects must satisfy all of the following criteria to be enrolled in the study:

1. The subject must read, understand, and sign the STATEMENT OF INFORMED CONSENT and receive a fully executed copy of the form
2. Appear able and willing to adhere to the instructions set forth in this clinical protocol
3. Between 18 and 35 (inclusive) years of age at the time of screening
4. The subject must be habitual contact lens wearers (defined as minimum 6 hours per day, 5 days a week over the last month)
5. The subject must meet all of the following three criteria:
 - a. The eye's spherical equivalent distance refraction must be in the range of -1.00 to -9.00 D (inclusive).
 - b. The eye's refractive cylinder must be less than or equal to -0.75 DC.
 - c. Each eye must have best corrected visual acuity of 20/25 or better.
6. The subject must have normal eyes (i.e., no ocular medications or infections of any type)

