5. TEST ARTICLE ALLOCATION AND MASKING

5.1. Test Article Allocation

The study lenses will be worn in a bilateral and random fashion using a 2x2 design. Permuted block randomization will be used to minimize the potential for bias in treatment allocation and to enhance validity of statistical comparisons across treatment groups. The randomization is such that on completion of the study visits each subject will have been tested under the 2 different treatments: AO1D, SCR. The subject will only be tested under a single treatment at each visit. The clinical site will follow the randomization scheme provided and will complete enrollment according to the randomization list and will not pre-select or assign subjects.

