6. STUDY INTERVENTION

6.1. Identity of Test Articles

The following contact lenses will be used in this study:

Table 1: Test Articles

	Test	Control
Test Article Form	Soft Contact Lens (best spherical equivalent)	Trial Frame of best corrected spherocylindrical refraction
Lens Name	ACUVUE OASYS® 1-Day with HydraLuxe™	NA
Product Type	Marketed	NA
Manufacturer	Johnson & Johnson Vision Care, Inc.	NA
Packaging Form	Blister Pack	NA
Lens Production Protocol Number	N/A	NA
Nominal Distance Powers	-1.00 to -6.00D in 0.25D steps and - 6.50 to -9.00 in .50D steps	As refracted on the day of visit
Material / main component of formulation	senofilcon A	NA
Nominal Water content (%)	38%	NA
Nominal Base Curve/Diameter Range @ 22°C (mm)	8.5/14.3	NA

There will be 2 lenses (one pair per subject) of AO1D used in this study. Therefore, for the 45 subjects in this study and giving room for lens replacements, approximately 100 lenses will be used.

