1.11	Subjective Sphero-cylindrical Refraction (SCR) LENSES OFF	
The investigator will complete subjective sphero-cylindrical refraction and then place in a trial frame and record the resultant distance Electronic LogMAR visual acuity (OD, OS and OU) to the nearest letter.
 
High Luminance (>400 lux) High Contrast for eLogMAR
	[REDACTED]

1.12	Subjective Best Sphere Refraction LENSES OFF	
Perform subjective best sphere refraction with a phoropter (adopt the maximum plus to maximum visual acuity (MPMVA) approach and use the duo-chrome test for binocular balancing). to achieveth best corrected distance visual acuity (OD, OS, OU) to the nearest letter.
 
Place refraction in a Trial Frame and record the resultant distance electronic LogMar visual acuity.
 
High Luminance (>400 lux) High Contrast for eLogMAR
 
Note: The endpoint criterion for the duo-chrome test is the lens power at which the red and green sides of the chart appear to be equally distinct. However, if the subject's response changes from "red" to "green" with only a 0.25 D change in power and no report that the two sides appear to be equally sharp, the refraction endpoint should be the lens power that leave the red chart sharper.
	
1.13	Slit Lamp Findings	
Efron Slit Lamp Classification Scale will be used to grade the findings and determine eligibility. If no slit lamp finding is noted on the EDC form it is considered as a zero "0" grade for all observations listed. If any of these slit lamp findings are Grade 3 or higher, the subject may not continue at this time, but may return up to one additional time to determine eligibility. If discontinued a final examination must be completed.
 
Should the clearance of the fluorescein need to be expedited, preservative-free rewetting drops may be instilled.
	Workaid: Efron Grading Scale Guideline
1.14	Eligibility after Baseline	All responses to Inclusion Criteria questions must be answered "yes" and all responses to Exclusion Criteria questions must be answered "no" for the subject to be considered eligible.	
1.15	Exit Distance Visual Acuity	Record the distance Snellen visual acuity with the subject's habitual lenses (OD, OS, and OU) to the nearest letter. Subjects must read the smallest line until at least 50% of the letters are read incorrectly.	
1.16		Schedule subject to return in 1-3 days	

VISIT 2

Subjects must not wear contact lenses on the day of this visit

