2.8	Subjective Lens Fit Assessment (if applicable)	
The lens fit will be judged to be either acceptable or unacceptable by the investigator based on centration, movement and other fitting characteristics.
 
An unacceptable fit is deemed by one of the following criteria:
 
 • limbal exposure at primary gaze or with extreme eye movement; • edge lift; • excessive movement in primary and up gaze; or • insufficient movement in all three of the following conditions: primary gaze, up gaze, and Josephson push up. 
Note: if lens fit is unacceptable subject will be discontinued from the study.
	 
2.9	Over refraction	Adjust the contact lens or trial frame lens power if the subject's best sphere over-refraction is not plano. Will allow +/-0.25 in the over refraction for -6.00 to -9.00.	
2.10	Lens Power Modification (if applicable)	
For each study lens power modification, repeat steps 2.5 - 2.9
 
Up to three power modifications are allowed.
	
2.11	Distance electronic LogMAR Visual Acuity	
Perform monocular distance Electronic LogMAR visual acuity test at a 4-meter distance OD and OS under the following conditions:
 
 1. bright illumination (e.g., >400 lux), high luminance with low contrast charts (HLLC) 2. dim illumination (e.g., <2.5 lux), low luminance (using neutral density filter), with high contrast charts (LLHC); 	M&S Work Aid 

2.12	qCSF	Perform monocular distance contrast sensitivity test with qCSF. Contrast sensitivity will be tested within the spatial frequency range of 1.5 to 18 cpd for the qCSF method. Area Under the Log CSF (AULCSF) and CSF Acuity will also be collected.	qCSF Work aid
2.13	TFI	Collect images	TFI Work aid
2.14	Lens Removal	Discard lenses after use	
2.15	Slit Lamp (if applicable)	Efron Slit Lamp Classification Scale will be used to grade the findings. Adverse events shall be documented and followed for significant slit lamp findings. If the clearance of the fluorescein needs to be expedited, preservative-free rewetting drops may be instilled.	Workaid: Efron Grading Scale Guideline
2.16	Exit VA	Record the exit distance Snellen visual acuity OD, OS, OU with habitual condition.	████████
2.17		Schedule subject to return in 1-3 days	

VISIT 3

Subjects must not wear contact lenses on the day of this visit

Visit #3 – Treatment #2 (1-3 days): SCR Electronic LogMAR Visual Acuity, QCSF			
Step	Descriptor	Details	████████ Appendix

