3.8	Subjective Lens Fit Assessment (if applicable)	
The lens fit will be judged to be either acceptable or unacceptable by the investigator based on centration, movement and other fitting characteristics.
 
An unacceptable fit is deemed by one of the following criteria:
 
 • limbal exposure at primary gaze or with extreme eye movement; • edge lift; • excessive movement in primary and up gaze; or • insufficient movement in all three of the following conditions: primary gaze, up gaze, and Josephson push up. 
Note: if lens fit is unacceptable subject will be discontinued from the study.
	
3.9	Over refraction	Adjust the contact lens or trial frame lens power if the subject's best sphere over-refraction is not plano. Will allow -0.25 in the over refraction for -6.00 to -9.00.	
3.10	Lens Power Modification (if applicable)	For each study lens power modification, repeat steps (3.5 – 3.9). Up to three power modifications are allowed.	
3.11	Distance electronic LogMAR Visual Acuity	Perform monocular distance Electronic LogMAR visual acuity test at a 4-meter distance OD and OS under the following conditions: 
 1. bright illumination (e.g., >400 lux), high luminance with low contrast charts (HLLC) 2. dim illumination (e.g., <2.5 lux), low luminance (using neutral density filter), with high contrast charts (LLHC); 	M&S Work Aid [REDACTED]
3.12	qCSF	Perform monocular distance contrast sensitivity test with qCSF. Contrast sensitivity will be tested within the spatial frequency range of 1.5 to 18 cpd for the qCSF method. Area Under the Log CSF (AULCSF) and CSF Acuity will also be collected.	qCSF Work aid
3.13	TFI	Collect images	TFI Work aid
3.14	Lens Removal	Discard lenses after use	

FINAL EVALUATION

The final evaluation will ordinarily take place immediately following the last scheduled follow-up visit per the study protocol. It may also take place at any point the subject discontinues the study or is terminated from the study.

Final Evaluation			
Step	Procedure	Details	
F.1	Final Exam Form	Indicate if the subject completed the study successfully. If subject discontinued from the study indicate the reason.	
F.2	Subjective spherocylindrical Refraction	Perform bare-eye subjective spherocylindrical refraction with a phoropter and record the best corrected distance Snellen visual acuity to the nearest letter (OD, OS, OU).	

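### Steps 2.9 and 3.9 set different over-refraction tolerances for -6.00 to -9.00 D, so the AO1D power permitted for a half-step eye depends on randomised order

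*Combined protocol and SAP*

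**What the plan says.** Steps 2.9 and 3.9 of Section 7.2 open with the same instruction, "Adjust the contact lens or trial frame lens power", which applies whenever the best-sphere over-refraction is anything but plano. The exception for high powers then differs:

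- Visit 2, step 2.9: "Will allow +/-0.25 in the over refraction for -6.00 to -9.00".
- Visit 3, step 3.9: "Will allow -0.25 in the over refraction for -6.00 to -9.00".

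Both visits can be the AO1D visit. Section 5.1 says "The subject will only be tested under a single treatment at each visit". Steps 2.5 and 3.5 each assign the treatment from the randomisation scheme and each carry contact lens instructions. They base the AO1D power on the Visit 1 best-sphere refraction but do not say how to round to an available lens.

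Table 1 (Section 6.1) lists AO1D in 0.25 D steps down to -6.00 D; beyond that the powers are "6.50 to -9.00 in .50D steps". The primary model in Section 14.5 has fixed effects for visit, test condition and sequence, and a random subject effect.

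**The concern.** The over-refraction step fixes the lens power in which the primary endpoint is measured. If the acceptance rule changes between visits, the sequence decides which rule governs the test lens. Among eyes with no exact lens, the AO1D-first group has a wider choice than the SCR-first group. A difference that affects both conditions at a visit is absorbed as a visit effect. One that affects only AO1D is not, and part of it passes into the AO1D-SCR difference compared with the 0.05 logMAR margin.

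A quarter dioptre is not obviously negligible here. Section 1 reports an earlier study with statistically significant acuity and contrast sensitivity differences against a positive control that was AO1D with +0.25 D added. It gives no effect size.

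**Working it through.** The plan gives no figure for this point, so there is none to reproduce. The check has four parts.

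**1. Which lenses each visit permits.** Over-refraction = required power minus lens power. Thirteen quarter-dioptre values run from -6.00 to -9.00 D. Seven exist as AO1D lenses (-6.00, -6.50, -7.00, -7.50, -8.00, -8.50, -9.00), and both visits permit the same lenses for them. Six do not:

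| Required power (D) | Less-minus lens (over-refraction -0.25) | More-minus lens (over-refraction +0.25) |
|---|---|---|
| -6.25 | -6.00 | -6.50 |
| -6.75 | -6.50 | -7.00 |
| -7.25 | -7.00 | -7.50 |
| -7.75 | -7.50 | -8.00 |
| -8.25 | -8.00 | -8.50 |
| -8.75 | -8.50 | -9.00 |

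Visit 2 accepts both columns. Visit 3 accepts only the less-minus lens.

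**2. What the model does with the difference.** Take -0.25 D at both visits as the reference. Let a = p_A x d_A be the mean shift in the AO1D results at Visit 2 and s = p_S x d_S the mean shift in the SCR results at Visit 2. Here p is the share of eyes tested with a +0.25 residual and d the resulting acuity change. Both Visit 3 cells have shift 0.

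- Treatment (AO1D - SCR): 1/2[(a - 0) + (0 - s)] = (a - s)/2
- Visit (V2 - V3): 1/2[(a - 0) + (s - 0)] = (a + s)/2
- Sequence means (AO1D-first minus SCR-first): (a + 0)/2 - (s + 0)/2 = (a - s)/2

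If a = s, the shift is purely a visit effect and the treatment estimate is unaffected. If s = 0, all three contrasts move by a/2, so the visit term does not clear the treatment estimate.

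**3. Size.** The documents give neither the power distribution nor d. Assumptions: required powers uniform over the 33 quarter-dioptre values from -1.00 to -9.00 D (the range in criterion 5a, Section 3.2); |d_A| up to 0.05 logMAR; s = 0, because trial-frame sphere can be brought to plano.

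- No vertex compensation: half-step share 6/33 = 0.182. If every such eye gets the more-minus lens at Visit 2, the shift is 0.182 x 0.05 / 2 = 0.0045 logMAR, and 0.0045/0.05 = 9% of the margin.
- If half of them do: 0.091 x 0.05 / 2 = 0.0023 (4.5%).
- If none do: 0.

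Appendix C (initial power determination) calls for vertex compensation beyond 4.00 D. With lens power = F/(1 - vF), at an assumed vertex distance v of 12 to 14 mm, a -9.00 D refraction needs -9.00/1.108 = -8.12 D at 12 mm and -9.00/1.126 = -7.99 D at 14 mm. Rounding compensated powers to the nearest quarter dioptre puts 4 of the 33 refractions on a half step at 12 mm, 6 at 13 mm and 4 at 14 mm. With 4 of 33, the upper end is 0.121 x 0.05 / 2 = 0.0030 logMAR (6%).

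The range is therefore 0 to about 0.003-0.0045 logMAR. With 42 completers (84 eyes), the upper ends correspond to 84 x 4/33 x 1/2 = 5.1 and 84 x 6/33 x 1/2 = 7.6 eyes in the more-minus lens. These counts illustrate the assumed distribution; they are not bounds.

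**4. Scale against sampling error.** If the 0.08 in Section 14.2 is the SD of the paired difference, the standard error with 84 independent eyes is 0.08/sqrt(84) = 0.0087. With an assumed between-eye correlation of 0.5 it is 0.08 x sqrt(1.5/84) = 0.0107. The middle case (0.0023) is about a quarter of a standard error and the upper end (0.0045) about half.

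**The case against.** The strongest reply is that step 2.9 permits the more-minus lens but does not require it. A reader might infer that two subjects with the same refraction will be tested 0.50 D apart purely because of their sequence. The text does not support that. A gap appears only if the investigator takes the more-minus option at Visit 2, and two AO1D-first subjects could also differ from each other by 0.50 D. An investigator who always takes the less-minus lens produces no sequence difference. Step 1.12 points that way for the refraction itself ("adopt the maximum plus to maximum visual acuity (MPMVA) approach"), which makes the upper end of the range less likely. This objection stands as a limit on size. It does not reconcile the two steps: the permitted set still differs by visit, and nothing tells the investigator which lens to use.

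A second reply is that step 3.9 was written for SCR only, since the Visit 3 table is headed "SCR Electronic LogMAR Visual Acuity, QCSF". Steps 3.5 to 3.8 rule this out: they assign treatment by randomisation and cover lens selection, insertion, settling and fit. The heading makes a drafting slip plausible, but the site would still follow step 3.9 as written.

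A third reply is that the sizing rests on assumptions about power distribution, vertex compensation and acuity effect. That is correct, and the range is conditional on them. On vertex distance, steps 2.5 and 3.5 mention adjustment only for the trial frame, so whether AO1D powers are compensated is left to the package insert.

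**Conclusion.** The inconsistency is real and sits in an operative rule. For a half-step eye between -6.00 and -9.00 D, the AO1D powers permitted depend on which visit randomisation gives to AO1D. Whether the power actually tested differs depends on the investigator's choice at Visit 2. To the extent that it does, and SCR does not shift with it, half of the mean AO1D shift at Visit 2 enters the treatment difference and the visit term does not remove it.

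The likely size is small: 0 to about 0.003-0.0045 logMAR on the assumptions stated, at most 6-9% of the margin, with unknown direction. It is zero if the less-minus lens is always used or if SCR shifts equally. A reader might infer that the non-inferiority conclusion is at risk; these numbers do not support that for this point alone. It is worth correcting because the rule sets the test-article power for the primary endpoint and the correction costs almost nothing.

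**What to change.** State the same tolerance in steps 2.9 and 3.9. Two versions work:

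- **-0.25 D only at both visits.** This fixes one lens for each half-step eye in either sequence. The cost is that those eyes are tested 0.25 D under-corrected with AO1D.
- **+/-0.25 D at both visits, with a rule for which of the two lenses to use**, for example the less-minus one. Without the rule, the permitted lenses match across visits but the choice stays with an investigator whom Section 5.2 does not describe as masked.

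Either version is a wording change to the over-refraction steps (a revision to one of them, plus a sentence of rule in both if the second is chosen). No visit time, data item or subject is added.

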7.3. Unscheduled Visits

If, during the investigation, a subject requires an unscheduled visit to the clinical site, the following information will be collected at a minimum:

- Chief complaint prompting the visit. If the reason is an adverse event, the applicable eCRF for the adverse event must be completed and subject record completed as appropriate
- Date and time of the visit and all procedures completed at the unscheduled visit
- Review of adverse event and concomitant medications
- Documentation of any test article dispensed or collected from the subject, if applicable
- Slit lamp findings (using the Slit Lamp Classification Scale)

If the Investigator withdraws a subject from the study, the final study visit case report forms must be completed indicating the reason(s) why the subject was withdrawn. The subject record must be completed documenting the date and primary reason for withdrawal and the study CRA notified.

Any ocular and non-ocular Adverse Events that are ongoing at the time of the study visit will be followed by the Investigator, within licensure, until they have resolved, returned to pre-

treatment status, stabilized, or been satisfactorily explained. If further treatment i.e., beyond licensure is required, the subject will be referred to the appropriate health care provider.

The following information will be collected during an unscheduled visit.

Step	Procedure	Details	
U.1	Chief Complaints	Record the subject's chief complaints for reasons for the unscheduled visit	
U.2	Change of Medical History and Concomitant Medications	Questions regarding the change of subjects' medical history and concomitant medications.	
U.3	Entrance VA	Record the entrance distance visual acuity (OD, OS and OU) to the nearest letter.	
U.4	Subjective Sphero-cylindrical Refraction	Perform bare-eye subjective sphero-cylindrical refraction with a phoropter (adopt the maximum plus to maximum visual acuity (MPMVA) approach and use the duo-chrome test for binocular balancing) and record the best corrected distance visual acuity to the nearest letter (OD, OS, OU).	
U.5	Slit Lamp Biomicroscopy	Efron Scale will be used to grade the findings. If no slit lamp finding is noted on the EDC form it is considered as a zero "0" grade for all observations listed. After the slit lamp examination, at the discretion of the Investigator, rinse the subject's eyes thoroughly with preservative-free saline.	Workaid: Efron Grading Scale Guideline
U.6	Exit Visual Acuity	Record the subject's exit distance visual acuity (OD, OS and OU) to the nearest letter	

7.4. Laboratory Procedures

No microbiology or laboratory testing required in this study.

See appended work-aid for Tear Film Interferometry image analysis.

8. SUBJECTS COMPLETION/WITHDRAWAL

8.1. Completion Criteria

Subjects are considered to have completed the study if they:

- provided informed consent;
- they are eligible:
 - have not withdrawn/discontinued from the study for any reason described in Section 8.2, and
 - completed all visits through the final visit. Subjects who did not complete visits 2 and 3 will not be considered to have completed the study.

8.2. Withdrawal/Discontinuation from the Study

A subject will be withdrawn from the study for any of the following reasons:

- Subject death during the study period
- Subject withdrawal of consent
- Subject not compliant to protocol
- Subject lost to follow-up
- Subject no longer meets eligibility criteria (e.g., the subject becomes pregnant)
- Subject develops significant or serious adverse events causing discontinuation of study lens wear
- Subjects who have experienced a Corneal infiltrative Event (CIE) deemed by the investigator to be a serious adverse event.
- Investigator's clinical judgment regarding the subject safety
- Subject missed two consecutive study visits

For discontinued subjects, the Investigator will:

- Complete the current visit (scheduled or unscheduled)
- Complete the Final Evaluation, indicating the reason that the subject was discontinued from the study
- Record the spherocylindrical refraction with best corrected distance visual acuity
- Collect used test article(s) (worn or brought to the visit) from the subject and discard them, unless otherwise stated in Section 7.2
- Collect all unused test article(s) from the subject

An additional subject will be enrolled if a subject discontinues from the study prematurely.

In cases where a subject is lost to follow-up, every possible effort must be made to contact the subject and determine the reason for discontinuation/withdrawal. The measures taken to follow up must be documented including two written attempts and a certified letter (or equivalent) as the final attempt.

9. PRE-STUDY AND CONCOMITANT INTERVENTION/MEDICATION

Concomitant medications will be documented during screening and updated during the study. Disallowed medications for this study include: *As indicated in exclusion criteria.*

Concomitant therapies that are disallowed include: *Lubricating eyedrops and drops that may affect the tear film (as determined by the investigator) are not allowed in this study.*

10. DEVIATIONS FROM THE PROTOCOL

Investigator will notify study sponsor upon identification of a protocol deviation. Major protocol deviations must be reported to the sponsor within 24 hours after discovery of the protocol deviation. The Investigator will report deviations per IRB/IEC requirements. All deviations will be tracked and corrective actions implemented as appropriate.

If it becomes necessary for the Investigator to implement a deviation in order to eliminate an immediate hazard to the trial subject, the Investigator may implement the deviation immediately without notification to the sponsor. Within 24 hours after the implemented deviation, the Investigator must notify and provide the rationale to the Sponsor and, as required, the IEC/IRB.

